### 9.7.11 Meta-analysis

Main estimates of association from the participating data sources will be pooled using meta-analytic techniques. Crude and/or adjusted IRs, PPs, cumulative incidence, IRRs, PPRs, and HRs along with 95% CIs will be estimated.

The heterogeneity across data sources will be checked, and a forest plot will be produced showing the data source-specific and pooled estimates. Using the main estimates from each data source, fixed- or random-effects meta-analytic methods will be used to obtain a combined effect estimate.

The analysis will be conducted and reported separately for each data source. The main estimates of association from the participating data sources will be pooled in the final report using meta-analytic techniques only if appropriate, based on a review of the effect measures, population characteristics, type and availability of data in the data sources included, and disease knowledge.

Some of the analysis may be limited due to a small number of events and/or data privacy driven cell count restrictions at each research partner.

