### 9.1.1 Retrospective Cohort Design

A retrospective cohort of exposed subjects will be selected. Subjects will enter the exposed cohort upon their first vaccination with AZD1222. Subjects in the AZD1222 cohort will be matched, as applicable, to 3 different comparator cohorts: concurrent unvaccinated subjects, active comparators (ie, subjects vaccinated with an mRNA vaccine against COVID-19), and historical comparators enrolled in the study data sources during the pre-pandemic period (ie, from 2017 to 2018). The AZD1222 cohort will be matched, as applicable, independently to the 3 different comparator cohorts on calendar date of vaccination, age, sex, region, prior COVID-19, and status according to each of the 5 special populations (Section 9.2.1.2). Propensity scores (PSs) will be used to address confounding, balancing multiple covariates such as comorbidities, markers of healthcare utilisation and comedication between the vaccinated and the different comparator cohorts (Austin 2014, Webster-Clark et al 2021). Relative risk will be the main measure of effect, which will be estimated using incidence rate ratios (IRRs), prevalence proportion ratios (PPRs), or hazard ratios (HRs), depending on the analysis and outcome. Absolute risk difference measures will include incidence rate differences, prevalence proportion differences (PPD), and  $1 - KM^2$  differences.

In the cohort study, the initial plan was to use concurrent, rather than historical, comparator (unvaccinated) subjects because they are at risk for COVID-19, and COVID-19 may function as an important covariable in the analyses of several of the safety endpoints. Moreover, both healthcare-seeking behaviours and healthcare delivery during the pandemic differ from those during the pre-pandemic era. The potential challenge with this approach is that during the pandemic, concurrent unvaccinated subjects in the comparator group may themselves become vaccinated over time. Results from Interim Reports 1 and 2 confirmed that the duration of follow-up among concurrent unvaccinated subjects was short (median, < 2 months in all data sources) and probably not long enough to evaluate AESIs with unknown risk window—(those with a risk window that ends at 180 or 365 days). Thus, additional comparators for whom the follow-up is expected to be longer were requested by the PRAC and have been added to the

---

[figure not shown]
 KM, Kaplan-Meier estimate.

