Note: Calculations assume a true IRR of 1.0 and a ratio of 1-to-1 exposed to unexposed PY. Calculations also assume that each person contributes 6 days of follow-up for anaphylaxis (3-day risk interval x 2 doses), 56 days for stroke (28-day risk interval x 2 doses), and 84 days (42-day risk interval x 2 doses) for all other adverse events. Calculations follow the method of Rothman and Greenland (2018).

AESI, adverse event of special interest; GBS, Guillain-Barré syndrome; IRR, incidence rate ratio; PY, person-years; RR, risk ratio; VAC4EU, Vaccine monitoring Collaboration for Europe; VTE, venous thromboembolism.

Third, for the outcome of TTS, study size implications were evaluated in terms of precision of the absolute risk difference, rather than IRR, because the background risk for this newly described syndrome is unknown and conceivably could be zero (Table 7). Relative risks cannot be quantified when the risk in the reference group is zero. Moreover, effect measures in terms of absolute risk are preferred to relative risk to assess the public health impact of a safety concern and how it may factor into benefit-risk balance. Among vaccinated individuals,

the risk has been estimated from reporting rates, which have ranged between 1 per 100,000 and 1 per 250,000 per vaccinee (WHO 2021). The duration of the risk period for TTS is not known, but for this exercise, it has been assumed to be 4 weeks; based on case reports published by 11 May 2021, the onset of this outcome appears to occur within 4 weeks of vaccination (Greinacher et al 2021, Scully et al 2021). Table 7 shows the probability that the upper 95% confidence limit of the absolute risk difference for TTS will fall below various thresholds, across a range of different study sizes, assuming a 1-to-1 ratio of vaccinated to unvaccinated subjects. For example, assuming that the true 4-week risk of TTS is 1 per 100,000 vaccinees and that the background risk is zero, with 1,000,000 people vaccinated there is a 99% probability that the upper confidence limit of the absolute risk difference will fall below 3.0 per 100,000.

**Table 7 Probability That the Upper 95% Confidence Limit of the Observed 4-Week Absolute Risk Difference for TTS Will Be Below Various Thresholds for Different Study Sizes, Assuming that a True 4-Week Risk Among Vaccinees is 1 per 100,000 or 1 per 250,000**

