### 9.7.7 Crude and Adjusted Measures of Association: Cohort Design

The analyses described below will address primary objective 4 and exploratory objectives 2.

- The analysis will compare subjects vaccinated with AZD1222 with the concurrent unvaccinated comparators and historical comparators to estimate the effect of receiving any dose (a first or a second), under the assumption that the effect of either dose is homogeneous. The effect of each individual dose on AESIs, will be estimated as prior vaccine exposure may “prime” the immune system.
- For outcomes that have **known risk windows**, we propose to estimate crude and adjusted IRRs and IR differences with 95% CIs using Poisson regression models. Specifically, the IRRs would be estimated using Poisson regression with robust estimation of the variance to account for individuals who may contribute person-time at different points to the exposed and unexposed cohorts (Zou 2004). For anaphylaxis and sudden death, crude and adjusted PPRs and PPDs with 95% CIs will be estimated using Poisson regression models with robust estimation of the variance to account for individuals who may contribute person-time to the exposed and unexposed cohorts at different timepoints.
- For outcomes **with unknown risk windows**, we propose estimating crude and adjusted relative risks and absolute risk differences. The relative risk (HRs) and 95% CI will be estimated using Cox regression models with robust estimation of the variance time-to-event analyses (Allison 2010). Using Cox regression models allows the flexibility to potentially adjust for time-dependant covariates, such as intercurrent COVID-19 infection.
- Adjustment for confounding will occur using PS, either through PS matching or by analytic methods involving stratification or weighting, which will be specified in the SAP. In the event that important covariates remain imbalanced after final selection of the cohorts for comparative analyses, additional approaches for confounding adjustment will be considered, including double-robust methods (ie, including the covariate in the outcome model as a separate term) or through analyses that restrict the population to subjects with more similar baseline characteristics (eg, subjects without substantial comorbidity).

The analysis described below will address exploratory objective 3

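### The list of pooled measures in Section 9.7.11 omits every risk and rate difference, although TTS was sized on the risk difference; the pooling of sparse ratios also needs a safeguard

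*Protocol*

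**What the plan says.** Section 9.7.11 opens with a general statement: "Main estimates of association from the participating data sources will be pooled using meta-analytic techniques". The next sentence names the measures: "Crude and/or adjusted IRs, PPs, cumulative incidence, IRRs, PPRs, and HRs along with 95% CIs will be estimated". It then describes the method: "Using the main estimates from each data source, fixed- or random-effects meta-analytic methods will be used to obtain a combined effect estimate". Pooling is to be done only if judged appropriate, and the section warns: "Some of the analysis may be limited due to a small number of events". No weighting method or zero-cell rule is given, and no database is excluded.

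Elsewhere the protocol plans difference measures. Section 9.1.1: "Absolute risk difference measures will include incidence rate differences, prevalence proportion differences (PPD), and" differences in 1 minus Kaplan-Meier. Section 9.7.7, for outcomes with known risk windows: "we propose to estimate crude and adjusted IRRs and IR differences with 95% CIs using Poisson regression models". Primary objective 4 (Section 8) covers relative and absolute risk.

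Section 9.5 explains why TTS was planned on the difference scale: "Relative risks cannot be quantified when the risk in the reference group is zero". It adds that "effect measures in terms of absolute risk are preferred to relative risk" when public health impact is assessed. Table 7 gives the resulting precision for 1 to 5 million vaccinees.

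**The concern.** The scale on which TTS precision was planned is missing from the scales on which results are to be combined. Under the zero background assumed in Table 7, no database has a TTS ratio to pool, and the difference is the only contrast that can be combined. Only CPRD exceeds 1 million matched vaccinees, and with 3,938,490 it falls short of the 4 and 5 million rows of Table 7. Those rows can be reached only by pooling.

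The second issue is the input to pooling, which is one estimate per database. For rare AESIs some databases will have no events in one cohort and so no finite log ratio. What happens to them then depends on a method that the protocol does not name, and some common choices would understate a true harm.

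**Working it through.** **1. The plan's own figures.**

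TTS (Table 7): with true risk p, zero background and N vaccinees, the probability that the upper 95% limit of the difference lies below U is Φ[(U − p)/√(p/N) − 1.96]. For p = 1 per 100,000 and N = 1,000,000 this gives 0.352 at U = 1.5 per 100,000 and 0.885 at U = 2.0 (Table 7: 0.35 and 0.89). At N = 5,000,000 and U = 1.5 it gives 0.942 (Table 7: 0.94).

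GBS (Table 5): Φ[ln U/√(1/a + 1/b) − 1.96], with a = 5,000,000 × 84/365.25 × 2/100,000 = 23.0 and b = a/3 = 7.67. At U = 3.0 this is Φ(1.0986/0.417 − 1.96) = 0.750 (Table 5: 0.75). The note under Table 5 states a different person-time ratio, but the figures reproduce with the 3:1 of its title, which is used below.

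Both tables therefore treat the stated number of vaccinees as one combined cohort.

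**2. TTS precision, pooled and by database.** The same formula was applied to the matched counts in Table 4, which sum to 5,557,094. U is 1.5 times the true risk.

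| Data | Matched vaccinees | True risk 1 per 100,000 | True risk 1 per 250,000 |
|---|---|---|---|
| All five | 5,557,094 | 0.96 | 0.65 |
| CPRD | 3,938,490 | 0.88 | 0.51 |
| SIDIAP | 609,842 | 0.23 | 0.12 |
| VID | 517,015 | 0.21 | 0.11 |
| ARS Toscana | 336,889 | 0.15 | 0.08 |
| PHARMO | 154,858 | 0.09 | 0.06 |

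Example, all five at 1 per 100,000: √(0.00001/5,557,094) = 1.34 per million; 5.0/1.34 = 3.73; Φ(3.73 − 1.96) = 0.96.

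**3. Zero cells for GBS.** Inputs from Section 9.5: 2 per 100,000 person-years, 84 days, person-time 3:1. Expected AZD1222 events are a = N × 84/365.25 × 2/100,000, and expected comparator events are b = a/3. At true IRR 1, P(zero in either cohort) = 1 − (1 − e^−a)(1 − e^−b).

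| Database | a | b | P(zero in either cohort) |
|---|---|---|---|
| CPRD | 18.12 | 6.04 | 0.002 |
| SIDIAP | 2.81 | 0.94 | 0.43 |
| VID | 2.38 | 0.79 | 0.50 |
| ARS Toscana | 1.55 | 0.52 | 0.68 |
| PHARMO | 0.71 | 0.24 | 0.89 |

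On average 2.5 of 5 databases have a zero cell. The probability that at least one does is 0.99.

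**4. Effect on a pooled GBS IRR.** Poisson simulation, 200,000 runs, five databases at the sizes above; medians shown.

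| Person-time | True IRR | Inverse variance, zero-cell databases dropped | Inverse variance, 0.5 added | Mantel-Haenszel |
|---|---|---|---|---|
| 3:1 | 1 | 0.89 | 0.91 | 1.00 |
| 3:1 | 2 | 1.67 | 1.73 | 2.04 |
| 3:1 | 3 | 2.46 | 2.53 | 3.05 |
| 1:1 | 1 | 1.00 | 1.00 | 1.00 |
| 1:1 | 2 | 1.92 | 1.94 | 2.00 |
| 1:1 | 3 | 2.83 | 2.87 | 3.00 |

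With databases dropped, the shortfall from the true value is 11 to 18% at 3:1 and 0 to 6% at 1:1. About 12% of events are lost at 3:1 and 4% at 1:1 (true IRR 1).

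**The case against.** Four arguments tell against the point.

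- **Differences may already be covered.** The opening sentence of Section 9.7.11 speaks of estimates of association, and Section 9.7.7, whose title uses that term, includes rate and prevalence differences. This stands in part: the list omits the differences but does not exclude them. The list is nevertheless explicit and comes directly after the general sentence, so an analyst following it would not pool them.
- **Absolute TTS risk is still available.** Pooled incidence is listed, and with zero background the risk in vaccinees equals the difference. This stands, but only at exactly zero background, which Section 9.5 itself calls unknown. A pooled contrast with its interval is still missing. Section 9.1.1 also makes relative risk the main measure, so the difference belongs beside the ratio and need not replace it.
- **The method is open.** A reader might infer that the protocol discards zero-event databases and so biases rare-event results toward the null. The text does not support this. It names neither inverse-variance weighting nor an exclusion rule, fixed- and random-effects methods include count-based ones, and Section 9.6.5 sends aggregated results to a central environment. The estimator may properly be left to the SAP. The direction is not uniform either: at true IRR 1 and 3:1 the median falls below 1.
- **Pooling is conditional.** A reader might also infer that the pooling method makes the study's main answer rest on one database. Results are reported by database, with pooling only if appropriate. CPRD holds 3,938,490 of 5,557,094 matched vaccinees (71%) and dominates under any method.

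**Conclusion.** The omission of difference measures from Section 9.7.11 holds. It conflicts with primary objective 4, with Sections 9.1.1 and 9.7.7, and with the scale on which Table 7 was built. It bears on whether a pooled TTS contrast is reported at all if comparator events are absent. At 1 per 100,000, the probability in section 2 of the working is 0.96 pooled against 0.88 in CPRD alone.

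The sparse-ratio point holds only as a conditional risk. It is material for the concurrent unvaccinated comparison at 3:1 if log ratios are combined by inverse variance, whether zero-cell databases are dropped or 0.5 is added. It is small at the 1:1 person-time assumed for the active and historical comparators. It does not show that the planned analysis is biased.

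Assumptions: the Interim Report 2 matched counts carry over to the final analysis (those for CPRD and ARS Toscana are preliminary); every vaccinee contributes 84 days for GBS; rates are equal across databases; estimates are crude. The TTS figures use the 4-week risk of Table 7, whereas the primary TTS window is 42 days, and they assume that all events and vaccinees are combined.

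**What to change.** 1. In Section 9.7.11, add incidence rate, prevalence proportion and 1 minus Kaplan-Meier differences with 95% CIs to the pooled measures. State that the pooled risk difference for TTS will be reported alongside any ratio. This costs one sentence, since the differences are already planned within each database.
2. For AESIs with few events in any database, state in the protocol or SAP that pooling will use a database-stratified Poisson or Mantel-Haenszel analysis of aggregated event counts and person-time, which keeps all databases. Inverse-variance meta-analysis can stay for common AESIs. Use counts for the pooled TTS difference too: at 1 per 250,000 PHARMO expects 0.62 events and has a 54% chance of none, and its estimated variance would then be zero.

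Costs: the stratified analysis assumes a common ratio across databases, small-cell privacy rules may limit some counts, and an adjusted version needs weighted counts with suitable variances from each database.

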### **9.7.12 Progress and Interim Analysis**

A first progress report was submitted to the regulatory agencies to update the status of the data source participation being explored at the time of the protocol endorsement, to confirm that data extractions and analysis as well as other study activities are being conducted as planned, and to discuss the impact of the changes in the uptake of the vaccine on the study and whether the inclusion of other databases should be explored. The second progress report, which replaced interim report 3, as agreed with EMA, will be delivered in April 2023, followed by the feasibility assessment report for the comparative analysis in June 2023.

Interim reports will include information from the study period available at the time of each data extraction, a description of the number of subjects vaccinated with 1 or 2 doses of AZD1222, the number of subjects vaccinated with one dose of AZD1222 and a second dose of another COVID-19 vaccine, IRs of the AESI, and comparative analyses (when the data have been accrued in the database and are available to support those analyses with sufficient precision).

The study periods to be included in each interim report will depend on the database, linkages, lag times, and the time required to obtain the data by the research institutions. In addition, for the first interim report, study period will also depend on time needed to allow for protocol endorsement by the EMA, contracting between research institutions, a minimum set of analytical instructions (or the whole SAP), data extraction, analysis, and reporting. For AESIs that require linkage with other databases such as hospital database or cause of death registers, time lags may be longer and may not be included in the first interim report.

Descriptions of the cohorts and estimations of IRs and any other measures will be performed as described in Section 9.7.

## 9.8 Quality Control

Rigorous quality-control (QC) procedures will be applied to all deliverables. Data transformation into the CDM will be conducted by each subcontracted research partner in its associated database, with processes as described in the following corresponding sections. Standard operating procedures or internal process guidance at each research centre will be used to guide the conduct of the study. These procedures include rules for secure and confidential data storage, backup, and recovery; methods to maintain and archive project documents; QC procedures for programming; standards for writing analysis plans; and requirements for scientific review by senior staff.

### CPRD, United Kingdom

The DSRU has information security policies in place to preserve the confidentiality, integrity, and availability of the organisation's systems and data by ensuring the following: the premises provide suitable physical and environmental security, all equipment is secure and protected against malicious software, the network can be accessed only by authorised staff, telecommunication lines to the premises are protected from interception by being routed overhead or underground, and personnel receive training regarding security awareness. The study will be conducted according to the *Guideline on Good Pharmacovigilance Practices (GVP)* ([EMA 2017b](#)) and according to the ENCePP Code of Conduct ([ENCePP 2018b](#)). Data quality is a high priority at the DSRU and is assured through a number of methods based on staff training, validated systems, error prevention, data monitoring, data cleaning, and documentation, including the following:

- Staff training on data processing standard operating procedures
- Data management plan for every research study outlining, eg, the legal basis for data collection, data flows, data access rights, data retention periods
- Routine data cleaning to screen for errors, missing values, and extreme values and diagnose their cause
- System process logs to document staff access and other items

### FISABIO, Spain

After Ethical Review Board approval, raw data will be extracted in text file format and will undergo a data quality check. Data will be stored on secure servers at FISABIO (Foundation for the Promotion of Health and Biomedical Research of Valencia Region) in accordance with Spanish and data protection requirements and ensuring that no identifiable data will be stored longer than required.

All the procedures that will be implemented for data collection, storage, protection, retention, and destruction will comply with national and EU legislation. The research team will stay up to date with the detailed provisions of the EU General Data Protection Regulation (GDPR),

which came into effect in May 2018, and which will supersede national legislation within the EU Member States.

### **SIDIAP, Spain**

Data quality processes will be implemented at each phase of the data flow cycle. Quality-control checks will be performed at the extraction and uploading steps. To assess data completeness, the elements present will be described by geographical areas, registering physician, time, and the distribution function of values. Correctness will be assessed by validity checks on outliers, out-of-range values, formatting errors, and logical date's incompatibilities. Completeness and correctness measures will be used to inform decisions on the required transformations to improve data quality (eg, harmonisation, normalisation, clean-up) and data fitness for the purpose of specific research projects.

### **ARS Toscana, Italy**

One or 2 researchers will review the study documents. ARS Toscana receives data on a bimonthly basis from the Tuscany region, and these data then undergo a first QC. The ARS Toscana statistical office appends the data to an Oracle database and checks them using a dashboard to identify any inconsistencies with historical data.

The Pharmacoepidemiology Unit has standardised parametric procedures in Structured Query Language (SQL) and Stata to extract data from the Oracle database. Parametric procedures are also available to convert the data into various CDMs. Study-specific procedures are developed, based on the study protocol and/or SAP, as well as by composing standard parametric procedures in Stata. Standard procedures in R are under development in the context of the ConcePTION project. The Unit also regularly generates simulated data sets and double programming in R programmes that are originally developed in SAS or Stata.

### **PHARMO, Netherlands**

PHARMO is ISO 9001:2015 certified for its quality management system. At the study level, all aspects of the study from protocol development to the reporting of the results are conducted within the work frame of the PHARMO quality management system.

The PHARMO Database Network combines data from different sources (eg, pharmacy, hospital, laboratory). These different sources are probabilistically linked through validated algorithms to ensure that patient privacy is maintained. Before databases are linked, those subjects for whom linkage-critical information (eg, date of birth, gender, GP) is missing are removed. All data are handled in a way that meets the full requirements for managing and storing sensitive patient data. Involved researchers have signed a confidentiality agreement. The anonymised data are stored on an internal network drive. Relevant extractions will be stored in a project folder. Specific checks on the linked data are performed, depending on

which data sources are used. The study data folder, including all extracted and derived data tables, will be archived after study closure.

All programming is developed in accordance with standard operating procedures, prepared by the lead analyst, and reviewed/quality controlled by an experienced analyst at PHARMO. Additionally, all results and reports are audited by the QC department, using a standardised check list.

The use of the PHARMO data is controlled by the independent Compliance Committee STIZON/PHARMO Institute. The Compliance Committee STIZON/PHARMO Institute consists of representatives of the participating data suppliers and a privacy expert (chairman of this Committee). Each study requires permission from this Committee, according to the applicable legislation in the Netherlands, eg, the Personal Data Protection Act and the Medical Treatment Contract Act. Within this legal framework, the Code of Conduct “Use of Data in Health Research” is an important document for the interpretation of the use of this kind of data for scientific research in the Netherlands and is approved by the Dutch Data Protection Authority ([www.dutchdpa.nl](http://www.dutchdpa.nl)).

